4. Describe the primary outcome variable(s), secondary outcome variables, and predictors and/or comparison groups as appropriate for the stated study objectives/specific aims.

Primary outcome variable: mean number of opioid tablets consumed 2 weeks postoperatively

Secondary outcome variables:

1. Patient reported opioid consumption 6 weeks postoperatively
2. Modified surgical pain score (validated questionnaire) at the preoperative assessment and 2 weeks and 6 weeks postoperatively
3. Responses to the Preoperative Opioid Education Study Survey (investigator authored) at the preoperative assessment
4. Responses to the Postoperative Opioid Education Study Survey (investigator authored) at 2 weeks

and 6 weeks postoperatively

5. Evaluate the number of opioid prescription refills postoperatively within the UC Irvine electronic medical record system and California Department of Justice CURES 2.0 database at 2 weeks, 6 weeks, 12 weeks, and 12 months postoperatively
6. Evaluate intraoperative complications (packed red blood cell transfusion, bowel injury, bladder injury, ureteral injury, conversion to laparotomy) – each variable will be measured independently
7. Evaluate postoperative complications (mesh exposure, wound infection, packed red blood cell transfusion, neuropathy, or urinary tract infection within 6 weeks postoperatively or return to the operating room for within 14 days post operatively) – each variable will be measured independently
8. Total daily morphine equivalents prescribed in the hospital prior to discharge – to be calculated using the Opiate Equianalgesic Dosing Chart
9. Post-operative date upon discharge from the hospital
10. Post-operative date that the patient passed a voiding trial and the transurethral catheter was removed
11. Duration of the surgery (in minutes)

Comparison groups: subjects will be randomized to an intervention arm versus control arm. The intervention arm will receive opioid informational pamphlets in addition to the standard preoperative and postoperative instructions and counseling. The control arm will receive the current standard preoperative and postoperative instructions and counseling. The two arms will be stratified by study site (UC Irvine versus Kaiser Permanente Orange County – Irvine).

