10. Post-operative date that the patient passed a voiding trial and the transurethral catheter was removed
11. Duration of the surgery (in minutes)

C. Research Procedures

1. Provide a detailed chronological description of all research procedures.

The study concept would be introduced to the patients at the consult visit, preoperative visit, on in the preoperative unit prior to surgery. If the patient agrees to participation during any of these encounters, written consent and HIPPA authorization will be obtained and the patient would be randomized to the intervention or control arm using a computerized randomization scheme on REDCap. The randomization will be stratified by the site of the surgery (UC Irvine Medical Center versus Kaiser Permanente Orange County – Irvine Medical Center). If the patient is randomized to the intervention arm, the first opioid informational pamphlet will be provided and reviewed with the patient in addition to standard preoperative instructions. If the patient is randomized to the control arm, standard preoperative instructions will be provided. Patients within both arms of the study will receive standardized postoperative medication prescriptions prior to the surgery. Patients within both arms of the study will complete the modified surgical pain score and preoperative opioid education study survey prior to surgery.

After the surgery is completed, the primary surgeon will decide whether to admit the patient to the hospital and which postoperative analgesics will be administered within the hospital prior to discharge for subjects in both study arms. The patient will follow up for standard postoperative clinic visits at 2 weeks and 6 weeks postoperatively. One to two days prior to the 2 week postoperative visit, the patient will be contacted via telephone to remind her to bring her opioid prescription bottle to the clinic visit.

Between the surgery date and the 2 week postoperative visit, the electronic medical records will be reviewed to evaluate the length of the surgery, intraoperative complications, the postoperative date of discharge, the postoperative date of removal of the transurethral foley catheter, the total daily morphine equivalents that the patient was prescribed prior to discharge from the hospital, and the presence of opioid prescriptions 30 days prior to the surgery. Additionally, the CURES 2.0 Database will be queried to evaluate for opioid prescriptions 30 days prior to the surgery.

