During the 2 week postoperative visit, the remaining opioid tablets will be counted and recorded by a co-investigator. The patient will complete the modified surgical pain score and postoperative opioid education study survey. The UC Irvine electronic medical record system and CURES 2.0 Database will be queried to evaluate for additional opioid prescriptions since the time of surgery. Patients randomized to the intervention arm will receive the second opioid informational pamphlet, which will be reviewed by a co-investigator.

During the 6 week postoperative visit, the patient will complete the modified surgical pain score and postoperative opioid education study survey. The UC Irvine electronic medical record system and CURES 2.0 Database will be queried to evaluate for additional opioid prescriptions since the time of surgery. The patients' electronic medical records will be reviewed after the 6 week postoperative visit to evaluate for postoperative complications.

Twelve weeks after the surgery, the UC Irvine electronic medical record system and CURES 2.0 Database will be queried to evaluate for additional opioid prescriptions since the time of surgery.

If a patient fails to follow up for a postoperative visit, at least two attempts will be made to contact the patient via telephone to collect opioid pill counts and have the patient verbally complete the modified

surgical pain score and postoperative opioid education study survey. Initial statistical analysis will be performed after the 12 week postoperative opioid refill assessment

Twelve months after the surgery, the UC Irvine electronic medical record system and CURES 2.0 Database will be queried to evaluate for additional opioid prescriptions since the time of surgery. Additional statistical analysis will be performed after the 12 month opioid refill prescriptions have been evaluated.

While this is a multi-site trial involving subjects from UC Irvine and Kaiser Permanente Orange County – Irvine, only deidentified data will be uploaded into the REDCap data management system. The lead investigator will maintain a separate key containing patient health information for subjects from both sites, which will be utilized to evaluate for additional opioid prescriptions 12 months after the surgery. Co-investigators from both study sites will not have access to identifiable data from subjects that were not recruited from their particular study site.

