Not applicable: Individual results will not be shared with subjects.

3. Describe whether overall study results will be shared with subjects.
4. Explain how results will be shared.

Not applicable: Final study results will not be shared with subjects.

I. Statistical Considerations

1. Statistical Analysis Plan: Describe the statistical method(s) for the stated specific aims and hypotheses. *Your analysis plans should match the stated study specific aims and hypotheses in Section 1.*

Not applicable: A statistical analysis plan is not appropriate for this qualitative study design. Plan for assessing study results:

2. Describe the primary statistical method(s) that will be used to analyze the primary outcome(s) or endpoints.

A t-test will be used to analyze the primary outcome, which will compare the mean number of opioid tablets consumed by subjects in the two study arms.

3. Describe the secondary statistical method(s) that will be used to analyze the secondary outcome(s) or endpoints.

A t-test will be used to compare the mean number of opioid tablets consumed at 6 weeks and 12 weeks postoperatively between subjects in the two study arms. A t-test will be used to compare the modified surgical pain score answers between subjects in the two study arms at the preoperative assessment, 2 weeks postoperatively, and 6 weeks postoperatively. Fisher's exact test will be used to compare the subjects' answers to standardized questions on the preoperative and postoperative opioid education study surveys (categorical response variables) between the two study arms. A Mann-Whitney test will be used to compare the number of opioid prescription refills at 2 weeks, 6 weeks, 12 weeks, and 12 months postoperatively between subjects in the two study arms. A Fisher exact test will be used to compare the rates of intraoperative and postoperative complications between subjects in the two study arms. A t-test will be used to compare the length of time to postoperative discharge, time to postoperative foley catheter removal, and length of the surgery between subjects in the two study

arms.

4. If appropriate describe secondary or post hoc analyses of primary outcome(s) or other exploratory analysis.

N/A

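### The documents give conflicting accounts of how 6-week opioid consumption is obtained, and specify no numeric source, for patients who attend, for the planned comparison of mean tablets

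*Combined protocol and SAP*

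**What the plan says.** Five parts of the combined protocol and SAP bear on the 6-week measure.

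- **Non-technical summary.** Consumption is assessed by physician-led pill counts at the postoperative clinic visits, in the plural and without restriction to week 2.
- **Endpoint lists (Section 1, item 4; Section 6.B, item 2).** Secondary outcome 1 is "Patient reported opioid consumption 6 weeks postoperatively". No unit, recall window or instrument follows.
- **Procedures (Section 6.C, item 1).** For week 2: "One to two days prior to the 2 week postoperative visit, the patient will be contacted via telephone to remind her to bring" her bottle, and "During the 2 week postoperative visit, the remaining opioid tablets will be counted and recorded by a co-investigator". For week 6: "During the 6 week postoperative visit, the patient will complete the modified surgical pain score and postoperative opioid education study survey", followed by queries of prescription records. For a missed postoperative visit, "at least two attempts will be made to contact the patient via telephone to collect opioid pill counts" and to complete the questionnaires verbally.
- **Instruments (Section 6.C, item 3).** The list holds the pain score and the two investigator-authored surveys.
- **Secondary analyses (Section 6.I, item 3).** "A t-test will be used to compare the mean number of opioid tablets consumed at 6 weeks and 12 weeks postoperatively". The same item assigns Fisher's exact test to answers on the "preoperative and postoperative opioid education study surveys (categorical response variables".

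Section 6.C, item 2 adds that at 12 weeks and 12 months only records are reviewed and patients are not contacted.

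**The concern.** A t-test on mean tablets needs a tablet number for every patient. The detailed procedures provide one at week 2 and do not say where it comes from at week 6 for a patient who attends. A number not collected at the visit cannot be recovered during analysis.

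Two risks to the comparison follow. First, attenders and non-attenders may be measured differently, so the 6-week mean would mix methods in proportions that depend on attendance. Second, if the value is self-report, it is given in an open-label trial. Only the intervention arm has by then received the second pamphlet, reviewed with a co-investigator at week 2. Any tendency to under-report after that session would act in the direction of the hypothesis.

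The outcome supports a stated aim. Section 1, item 3 compares the pattern of consumption at 2 and 6 weeks and hypothesises that educated patients are less likely to take tablets after week 2.

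**Working it through.** **1. The plan's own figure.** The only computed figure is the sample size for the primary outcome (Section 6.I, item 5). The inputs are a difference of 5 tablets, an SD of 10 (implied by 5 tablets = 0.5 SD), significance level 0.05 (two-sided assumed, as the plan does not say) and 80% power. Then n = 2 × (1.960 + 0.842)² × (10/5)² = 62.8, so 63 per arm, as stated. The normal approximation gives 80.1% power at 63 and the exact t-test gives 79.5%. For attrition, 63 × 1.15 = 72.45, so 73, as stated; 63/0.85 = 74.1 would give 75. None of these figures uses the 6-week measure, so this point changes none of them.

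**2. The accounts of the 6-week measure side by side.**

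| Place | Source of 6-week consumption | Gives a tablet number for attenders? |
|---|---|---|
| Non-technical summary | Pill count at postoperative visits | Yes, if it includes week 6 |
| Section 1, item 4; Section 6.B, item 2 | Patient report | Not stated |
| Section 6.C, item 1, attenders | Pain score, survey, record queries | None listed |
| Section 6.C, item 1, missed visit | Pill count by telephone | Not applicable |
| Section 6.C, item 3 | Pain score and surveys | Survey items not shown |
| Section 6.I, item 3 | Mean tablets, t-test | Required |

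The analysis needs a number that the procedures do not list for attenders. The record queries yield prescriptions, not tablets taken. The only data type the plan gives for the survey questions is categorical.

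**3. Attendance.** Read literally, a patient who misses week 6 is asked for a pill count, while one who attends completes a survey of unstated content. The method then depends on attendance.

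**4. What a week-6 count must handle.** Consumption inferred from a bottle is tablets supplied minus tablets remaining minus tablets disposed of. If disposal is ignored, each disposed tablet is scored as consumed, and the difference between arms is distorted by the difference in mean tablets disposed of. The plan hypothesises better disposal in the intervention arm (Section 1, item 3). An uncorrected count could therefore bias the comparison against the intervention.

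**5. The 12-week comparison.** The sentence that sets the 6-week t-test also covers mean tablets at 12 weeks. Section 6.C, items 1 and 2 provide only record queries then, with no patient contact. Refills can be counted from that source; tablets consumed cannot.

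**The case against.** The strongest reply is that this is a drafting gap. The postoperative survey is not reproduced and may contain a numeric tablet question. The plan lists patient-reported consumption separately from survey responses and gives the two different tests, so it treats consumption as a numeric variable of its own. The summary's plural visits and the telephone pill counts suggest that a 6-week count may simply have been left out of one paragraph. A declared patient-reported endpoint is also a legitimate choice. All of this stands. A reader might infer that 6-week consumption is not measured, or that attenders give only categorical answers; the documents do not support either statement.

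The likely harm can also be overdrawn. No section plans to subtract the 2-week value from the 6-week value, and the hypothesis about use after week 2 is a yes/no question that a categorical report could answer. A reader might argue that recall error would be as large as the tablets used between the two visits, but the documents give no figure for use in that interval or for recall error. If the measure is cumulative, random error costs little. Assuming that the SD of 10 carries over and that recall error is independent with SD 3, the total SD is √(10² + 3²) = √109 = 10.4.

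This reply does not remove three problems. The sections still disagree, the method may still differ by attendance, and the calculation above covers random error only. It says nothing about error that differs between arms.

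**Conclusion.** The point holds as an inconsistency with a practical consequence: the documents describe the 6-week measure in conflicting ways and specify no numeric source for attenders for the planned mean. It concerns one secondary outcome, and up to the 63 patients per arm expected to complete. The primary outcome has a specified tablet count, and the sample size is unaffected.

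The size of any bias cannot be calculated from the documents. Under-reporting that favours the intervention is possible, because the trial is open-label and one arm is taught again at week 2, but it is not shown. The conclusion rests on reading Section 6.C, item 1 as the full list of procedures, which is what its prompt asks for. If the survey does contain a numeric tablet item, the numeric source exists. The plan would still need to name it, give its unit and window, and reconcile the summary and the telephone procedure with it.

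The point deserves action before data collection, because missing week-6 counts cannot be restored later. The 12-week comparison is the clearer gap: no patient contact is planned from which tablets consumed could be obtained.

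**What to change.** - In Section 6.C, item 1, extend the reminder call and the tablet count to the 6-week visit, done as at week 2.
- At that visit record tablets disposed of since week 2 and any new or earlier opioid supply. Disposed tablets are then not counted as consumed. An empty bottle with no new prescription should not be scored zero automatically: preoperative opioid users are eligible and may hold earlier supplies.
- Define 6-week consumption as cumulative, namely the 2-week value plus use since then, with unit and time window stated.
- Use the same items for attenders and for patients reached by telephone, and flag self-reported values.
- Align the non-technical summary, Section 1, item 4, Section 6.B, item 2, Section 6.C, item 1 and Section 6.I, item 3.
- Remove the 12-week comparison of mean tablets, or limit week 12 to the refill comparison already planned.

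The cost is one more call per patient and a few minutes of counting at a visit that already takes place. Some patients will not bring the bottle, and disposal will still be self-reported, so the change reduces reliance on unblinded report without removing it.

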1. Include an explanation of the study design (e.g., randomized placebo-controlled, cross-over, cross-sectional, longitudinal, etc.) and, if appropriate, describe stratification/ randomization/blinding scheme.

Randomized, non-blinded, controlled trial. Patients will be randomized into intervention (specific patient opioid education performed) and control (standard of care without specific patient opioid education) arms through a randomization scheme in REDCap. Randomization will be stratified by medical center (UC Irvine Medical Center versus Kaiser Permanente Orange County – Irvine Medical Center). Patients and providers will not be blinded due to the nature of the intervention (educational).

2. Provide precise definitions of the study endpoints and criteria for evaluation; if the primary outcomes are derived from several measurements (i.e., composite variables) or if endpoints are based composite variables, then describe precisely how the composite variables are derived.

Primary outcome: mean number of opioid tablets consumed 2 weeks postoperatively

Secondary outcome variables:

1. Patient reported opioid consumption 6 weeks postoperatively
2. Modified surgical pain score (validated questionnaire) at the preoperative assessment and 2 weeks and 6 weeks postoperatively
3. Responses to the Preoperative Opioid Education Study Survey (investigator authored) at the preoperative assessment
4. Responses to the Postoperative Opioid Education Study Survey (investigator authored) at 2 weeks and 6 weeks postoperatively
5. Evaluate the number of opioid prescription refills postoperatively within the UC Irvine electronic medical record system and California Department of Justice CURES 2.0 database at 2 weeks, 6 weeks, 12 weeks, and 12 months postoperatively
6. Evaluate intraoperative complications (packed red blood cell transfusion, bowel injury, bladder injury, ureteral injury, conversion to laparotomy) – each variable will be measured independently
7. Evaluate postoperative complications (mesh exposure, wound infection, packed red blood cell transfusion, neuropathy, or urinary tract infection within 6 weeks postoperatively or return to the operating room for within 14 days post operatively) – each variable will be measured independently
8. Total daily morphine equivalents prescribed in the hospital prior to discharge – to be calculated using the Opiate Equianalgesic Dosing Chart
9. Post-operative date upon discharge from the hospital

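### Randomisation is stratified by site but no analysis includes site, and the 2- and 6-week pain comparisons ignore the preoperative score; the tests stay valid, at a modest cost in precision

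*Combined protocol and SAP*

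**What the plan says.** The design is stated consistently. Section 1 item 4 says "The two arms will be stratified by study site", Section 6.B item 1 says "Randomization will be stratified by medical center", and Section 6.C item 1 says "The randomization will be stratified by the site of the surgery". There are two sites.

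The analysis does not follow the design. For the primary outcome, Section 6.I item 2 says "A t-test will be used to analyze the primary outcome, which will compare the mean number of opioid tablets consumed" by arm, and nothing more. Item 4 of the same section, where the form asks "If appropriate describe secondary or post hoc analyses of primary outcome(s) or other exploratory analysis", is answered as not applicable. No site term appears in items 2 or 3.

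For pain, Section 6.I item 3 says "A t-test will be used to compare the modified surgical pain score answers between subjects in the two study arms at the preoperative assessment" and again at 2 and 6 weeks. These are three separate comparisons, and the first is not used in the other two. The preoperative score is itself part of a listed secondary outcome in Section 6.B item 2: "Modified surgical pain score (validated questionnaire) at the preoperative assessment and 2 weeks and 6 weeks postoperatively". On its timing, Section 6.C item 1 says only "Patients within both arms of the study will complete the modified surgical pain score and preoperative opioid education study survey prior to surgery", in a sentence that comes after the description of randomisation and pamphlet review.

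**The concern.** Stratifying by site makes the arms nearly balanced within each site, so a difference in tablet use between sites cannot bias the arm comparison. The ordinary t-test does not know this. It leaves the between-site variation in its standard error, although the design has already removed that variation from the treatment estimate. The result is a test that rejects less often than 5% under the null and an interval wider than the data warrant. A site term corrects both.

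The same reasoning applies to pain. A score taken before randomisation that predicts later scores would remove part of the residual variance. Here the loss depends on the correlation between preoperative and postoperative scores, not on site. The wording on timing adds a second difficulty: a score taken after the pamphlet has been reviewed is not a baseline, and a difference between arms in it could be chance or an effect of the pamphlet.

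Precision has little slack, because the sample size leaves no reserve above 80% power. Prespecification also matters. The trial is unblinded, and a site-adjusted result that first appears after the data are seen would look post hoc.

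**Working it through.** **Inputs from the documents.** Section 6.I item 5 gives a difference of 5 tablets equal to 0.5 SD, hence SD = 5/0.5 = 10 tablets. It also gives significance level 0.05, power 80%, 63 per arm, 15% attrition and 73 recruited per arm. Sidedness is not stated. Two-sided is assumed because it reproduces 63; a one-sided test would need 50.

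**The plan's own figure.** Under the normal approximation, n per arm = 2 × (1.960 + 0.842)² × 10² / 5² = 62.8, rounded up to 63. This matches. The noncentral t distribution gives 79.5% power at 63 per arm.

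**Expected completers.** 73 × 0.85 = 62.05, so 62 per arm. (The stated 73 is 63 × 1.15 = 72.45 rounded up; 63/0.85 = 74.1 would call for 75.) Power at 62 per arm is 78.9%.

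**Assumptions, because the documents are silent.** The site gap and the site shares are not given. Total SD is held at 10, arms are balanced within site, and w is one site's share of patients.

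**Site term.**
- Share of variance due to site: R² = gap² × w(1 − w) / 100.
- True type I error of the t-test: 2 × P(T₁₂₂ < −1.980/√(1 − R²)).
- Width of the t-test interval relative to what is needed: 1/√(1 − R²).
- Power: noncentrality is 0.5 × √(62/2) / √(1 − R²) = 2.784/√(1 − R²). The unadjusted test uses the critical value 1.980/√(1 − R²) on 122 degrees of freedom. The adjusted test uses 1.980 on 121.

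Example, equal sites and a 4-tablet gap: R² = 16 × 0.25/100 = 0.04 and √0.96 = 0.980. The effective critical value is 1.980/0.980 = 2.020, which gives a type I error of 0.0455. The noncentrality is 2.784/0.980 = 2.841, which gives power 79.3% unadjusted and 80.5% adjusted.

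| Gap (tablets), equal sites | R² | t-test type I error | Interval ratio | Power, t-test | Power, with site | Gain (points) |
|---|---|---|---|---|---|---|
| 0 | 0 | 0.0500 | 1.000 | 78.9% | 78.9% | −0.01 |
| 2 | 0.01 | 0.0489 | 1.005 | 79.0% | 79.3% | 0.3 |
| 4 | 0.04 | 0.0455 | 1.021 | 79.3% | 80.5% | 1.1 |
| 6 | 0.09 | 0.0401 | 1.048 | 80.0% | 82.5% | 2.6 |

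With an 80/20 split, gaps of 2, 4 and 6 gain 0.2, 0.7 and 1.6 points. Larger gaps gain more: 4.5 points at 8 tablets and 8.0 at 11 (equal sites). For scale, 11 tablets is the whole width of the 2–13 range of literature means in Section 6.I item 5. That range does not bound the gap between these two sites.

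**Simulation check.** With 100,000 trials per case, equal sites and gaps of 2, 4 and 6, power was 0.790, 0.793 and 0.799 for the t-test and 0.793, 0.805 and 0.825 with site. Type I error was 0.050, 0.045 and 0.041 for the t-test and 0.050 to 0.051 with site. A separate simulation at 63 per arm with skewed counts showed the same pattern. The t-test's type I error fell from 0.052 with no gap to 0.030 at 10 tablets, and the adjusted test stayed between 0.046 and 0.052.

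**Pain scores.** The correlation r between preoperative and later scores is not given. Site is included in the model but assumed to explain nothing. The width of the adjusted interval relative to the t-test's is √((1 − r²)(1 + 1/120)) × t₀.₉₇₅,₁₂₀ / t₀.₉₇₅,₁₂₂. For r = 0, 0.2, 0.3 and 0.5 this is 1.004, 0.984, 0.958 and 0.870: 0.4% wider, then 1.6%, 4.2% and 13.0% narrower.

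**The case against.** The case against is mainly about weight. The planned test never exceeds 5% type I error, no estimate is biased, and no figure in the documents shows that the sites differ at all. For gaps up to 6 tablets the gain is at most 2.6 points. All of this stands, and it is why the point is modest.

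The argument from thin power is also weaker than it looks. The enrolment table in Section 3.A expects 63 completers per arm, not 62. The shortfall comes from how attrition was applied, not from the missing site term. With total SD fixed at 10, the unadjusted t-test itself reaches 80.0% at a 6-tablet gap. These points are fair: the site term is not needed to rescue the power. The reason to add it is that it restores the stated 5% level and the correct interval width, at almost no cost.

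On pain, one can say that not adjusting is the safer choice while the score may be taken after the pamphlet. That is right for the protocol as written, and adjustment should depend on fixing the timing. At correlations of 0.2 or less the benefit is negligible. Finally, the not-applicable answer in Section 6.I item 4 says little by itself, since that item does not ask about covariates in the primary model. It shows only that no adjusted analysis is supplied there.

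**Conclusion.** The concern holds, as an improvement that should be made and not as a threat to the primary conclusion. The analysis omits the factor by which the trial randomises. The planned t-test is valid, but it is conservative if sites differ. With equal sites and gaps of 2 to 6 tablets, its true level is 4.9% to 4.0%, its interval is 0.5% to 5% too wide, and it gives up 0.3 to 2.6 points of power. If the sites do not differ, nothing is lost. The loss on the pain outcomes ranges from none to a 13.0% narrower interval forgone as the correlation goes from 0 to 0.5. These sizes rest on assumed site gaps, site shares and correlations, a total SD of 10 and 62 completers per arm. The mismatch between design and analysis does not depend on those assumptions, nor does the unfixed timing of the preoperative pain score.

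**What to change.** 1. In Section 6.I item 2, make the primary analysis a linear model of tablets consumed on arm and site, and keep the t-test as a sensitivity analysis.
2. In Section 6.I item 3, analyse the 2- and 6-week pain scores by analysis of covariance on the preoperative score and site.
3. In Section 6.C item 1, state that the preoperative pain score is completed before randomisation. Keep it as a listed outcome reported by arm; descriptive reporting is enough once it is a true baseline. The preoperative survey can stay as planned, since the documents do not say whether it is meant as a baseline.

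The cost is analysis-plan wording plus one procedural sentence. That sentence affects the timing of a listed outcome and so needs a protocol amendment. No extra patients are needed, and each covariate uses one degree of freedom.

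Prior opioid use could be added as one further prespecified covariate, since Section 1 item 3 expects it to raise consumption. This is optional. Consent can occur at any point from the consult visit to the preoperative unit, so the planned 30-day look-back from surgery may run past randomisation. The covariate should instead use prescriptions dated before randomisation and exclude the study's own postoperative prescription, which is issued before surgery. That requires a second look-back window and may be less predictive when consent is early. In simulation with assumed prevalence and effect, the change ranged from a loss of about 0.2 points of power (5% prevalence, 2 more tablets) to a gain of 5.0 (30%, 8 more tablets). If neither site nor prior use is prognostic, adding both loses about 0.3 points.
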